### 9.4.2 SAFETY ANALYSES

Analysis of treatment-emergent AEs will be conducted based on the safety population. Safety endpoints include:

- AEs
- Concomitant medications
- Heart rate and blood pressure
- BCVA
- IOP
- Biomicroscopy
- Conjunctival hyperemia

Ocular events will be reported on an eye level, while non-ocular events will be on a patient level.

AEs will be coded using the Medical Dictionary for Regulatory Activities (MedDRA). For each AE reported, the number and percent of patients/eyes will be tabulated based on the preferred term and ocular and non-ocular AEs will be reported separately. The tables will be generated by relationship to treatment as well as by system organ class and severity.

The primary safety endpoint is the AE rate ( $100 \times [\text{number of AEs} / \text{number of eyes exposed to treatment}]$ ). The modified safety set will be used for a sensitivity analysis of the primary safety endpoint.

*Secondary safety endpoints:*

- Percent of patients with  $\geq 5$ -mmHg increase from baseline in IOP at each visit
- Abnormal slit-lamp biomicroscopy findings at the Baseline, Day 1, and Day 7 Visits
- Contact lens protein deposits at the Day 7 Visit
- Change from baseline in CLDEQ-8 results at the Day 7 Visit

Pre-existing AEs, those identified after enrollment but before treatment with LL-BMT1, will be tabulated for all consented patients.

---

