### 3 OBJECTIVES AND ENDPOINTS

Objectives	Endpoints	Justification for Endpoints
Primary safety		
To evaluate the safety of LL-BMT1 in patients with POAG or OHT	AE rate	AE collection is necessary to determine the safety of this intervention. AEs will be collected at each visit to maximize safety during the study.
Secondary safety		
To evaluate the safety and tolerability of LL-BMT1 in patients with POAG or OHT	The secondary safety endpoints are: 
 
• Percent of patients with <math>\geq 10</math>-mmHg increase from baseline in IOP at each visit
 
• Abnormal slit-lamp biomicroscopy findings at the Baseline, Day 1, and Day 7 Visits
 
• Contact lens protein deposits at the Day 7 Visit
 
• Change from baseline in CLDEQ-8 results at the Day 7 Visit
 
	These safety endpoints will provide additional safety information during the course of the study.
Secondary efficacy		
To evaluate IOP-lowering effects of LL-BMT1 in patients with POAG or OHT	The secondary efficacy endpoint is: 
 
• Change from baseline in IOP at each visit
 
	IOP assessment is necessary to determine the efficacy of an IOP-lowering device.

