### 8.2 SAFETY AND OTHER ASSESSMENTS

Abnormal findings that are of clinical significance will be recorded as AEs on the eCRFs.

- **Ultrasound pachymetry.** Corneal thickness will be measured using an ultrasound pachymeter.
- **Humphrey visual field assessment.** Visual field (perimetry) will be assessed using a Humphrey Field Analyzer. If Humphrey visual field assessment has been completed within 6 months of Screening Visit, it does not have to be repeated at the Screening Visit
- **Contact Lens (CL) Assessment:** Assessments will include contact lens centration, movement with blinking, and lens surface wettability/deposits, as described in ISO 11980:2012.
- **Heart rate and blood pressure.** Heart rate and blood pressure will be measured by a manual or automated sphygmomanometer.
- **Pregnancy testing.** Pregnancy testing will be performed using a human chorionic gonadotropin pregnancy urine dipstick test on women of childbearing potential.
- **Best-corrected visual acuity.** BCVA will be quantified using the ETDRS visual acuity protocol (at a distance of 3 m) and the number of letters read correctly will be recorded on the eCRF.
- **Biomicroscopy.** Biomicroscopy will be performed by slit-lamp examination of conjunctiva, cornea, and iris with findings reported on a scale of 0 = none, 0.5 = trace, 1 = mild, 2 = moderate, and 3 = severe. The status of the lens will be assessed using the Age-Related Eye Disease Study scale.
- **Goldmann applanation tonometry.** IOP will be measured with a Goldmann applanation tonometer. During the study, the LL-BMT1 contact lens will be removed in order to perform IOP assessment. Of particular significance, all lens insertions and removals will be conducted by the investigator. IOP will be assessed 3 minutes after lens removal, with the goal of reinserting the lens within 5 minutes of removal. Two consecutive IOP measurements of each eye were obtained. If the 2 measurements differed by more than 2 mmHg, a third measurement was obtained. For each eye, IOP was analyzed as the mean

of 2 measurements or as the median of 3 measurements. For each patient, change from baseline IOP was determined by averaging the values for each eye (Sherwood 2006).

- **Conjunctival hyperemia.** The Efron Grading Scales for Contact Lens Complications will be performed using a conjunctival hyperemia scale.

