## 9.4 STATISTICAL ANALYSES

### 9.4.1 GENERAL APPROACH

The database will be locked after all patients exit the study and all data clarification forms or queries have been resolved. Prior to database lock, a detailed Statistical Analysis Plan (SAP) will be finalized and approved. Final analysis will occur after database lock.

Wherever appropriate, summary statistics will include the frequency, mean, standard deviation, median, minimum, and maximum for continuous and ordinal variables, and frequency counts and percent for categorical variables. Graphical representations of the results may also be provided.

In general, unless otherwise specified, eyes will be the analytical unit and a formal statistical test will only be conducted for exploratory purposes when sample size is deemed appropriate. All testing will be two-sided with a 95% confidence level. Due to the small sample size in this study, nonparametric approach will be applied. For quantitative variables, within-eye before-and-after comparisons will be assessed using one-sample Wilcoxon test. For qualitative variables, Fisher's Exact test will be used.

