6.8 Secondary Analysis

There will be both safety and efficacy assessments in the secondary analysis.

The secondary safety analysis will consist of identifying the following:

- Percent of patients with ≥ 5 mmHg increase from baseline in IOP at each visit
- “Abnormal” and “Severe” slit-lamp biomicroscopy findings at the Baseline, Day 1, and Day 7 Visits
- Contact lens protein deposits at the Day 7 Visit
- Change from Baseline in CLDEQ-8 results at the Day 7 Visit

The secondary efficacy analysis will consist of identifying the change from baseline in IOP at each visit. Study eyes only within the modified intent-to-treat population will be used for this part of the analysis.

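### The patient-level IOP-rise safety endpoint has no rule for combining two treated eyes; the only per-patient rule in the documents averages them and, if applied, can undercount one-eye rises

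*Protocol*

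**What the plan says.** **The endpoint.** SAP 6.8 gives it as "Percent of patients with ≥ 5 mmHg increase from baseline in IOP at each visit", and SAP 5.2 lists the same item. The Protocol synopsis and Protocol 9.4.2 also use patients and 5 mmHg; 9.4.2 words it as an "increase from baseline in IOP at each visit" of at least that size. The table in Protocol Section 3 has the same endpoint with a cut-off of 10 "mmHg increase from baseline in IOP at each visit". None of these places says whether a patient counts on the study eye, either eye, both eyes or their mean.

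**The eyes.** Protocol 4.1 has both eyes treated and each eye tested separately, and restricts the efficacy analysis to the study eye. Protocol 9.4.3 and SAP 6.8 repeat that restriction, again for efficacy only.

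**The combining rule.** The tonometry paragraph of Protocol 8.2 first deals with readings within an eye: two are taken, and "If the 2 measurements differed by more than 2 mmHg, a third measurement was obtained". The eye's value is the mean of two or the median of three. It then moves to the patient: "For each patient, change from baseline IOP was determined by averaging the values for each eye".

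**The general rules.** Protocol 9.4.1 says "In general, unless otherwise specified, eyes will be the analytical unit". Protocol 9.4.2 says "Ocular events will be reported on an eye level, while non-ocular events will be on a patient level". The SAP contains no rule for combining eyes, and SAP 1.1 records no changes from the protocol.

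**The concern.** A percentage of patients needs a function that turns two eyes into one yes or no. Here that function is not stated at the endpoint, and the candidates give different answers from the same data. The one explicit per-patient rule halves a rise confined to one eye and lets a fall in the other eye offset it. That may suit a measure of average effect, but it suits a count of pressure elevations poorly. Borrowing the study-eye rule would instead discard a treated eye.

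Safety is the primary objective, the study is open-label and only five patients are treated. A rule chosen after the data are seen could move the reported percentage by a visible step.

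**Working it through.** **Inputs from the documents.** T = 5 mmHg (Protocol 9.4.2, SAP 6.8) or 10 mmHg (Protocol Section 3); five treated patients (Protocol 9.2); mean of the two eyes (Protocol 8.2). The documents give no expected value for this endpoint, so there is no planned figure to reproduce. The fellow-eye change f is not given either, so a range is assumed.

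**Step 1: which rule would an analyst find?**

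| Candidate | Where | Does it fit this endpoint? |
|---|---|---|
| Eye as unit | Protocol 9.4.1 | Yields to any other stated unit; this endpoint names patients |
| Eye level for ocular events | Protocol 9.4.2 | Introduces the adverse event tables; does not define a patient count |
| Study eye only | Protocol 4.1, 9.4.3; SAP 6.8 | Stated for efficacy only |
| Mean of two eyes | Protocol 8.2 | Per patient, change from baseline, in the safety assessments section; not tied to this endpoint by name |

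The sentence in 8.2 is unlikely to mean averaging of readings within an eye, because the sentence before it already covers that.

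**Step 2: condition for a missed rise.** Let a be the rise in one eye. The patient is not counted when (a + f)/2 < T, that is, when a < 2T − f.

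| f (mmHg) | Missed below, T = 5 | Missed below, T = 10 |
|---|---|---|
| 0 | 10 | 20 |
| −3 (assumed) | 13 | 23 |
| −4 (assumed) | 14 | 24 |
| −5 (assumed) | 15 | 25 |

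**Step 3: examples at T = 5.**

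| Eye changes (mmHg) | Mean | Counted by mean? | Counted by either eye? |
|---|---|---|---|
| +9.9, 0 | 4.95 | no | yes |
| +12, −4 | 4.0 | no | yes |
| +10, 0 | 5.0 | yes | yes |

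Under a study-eye rule, each of these patients is counted only if the rising eye happens to be the study eye.

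**Step 4: direction.** If both eyes are below T, their mean is below T. A mean of at least T therefore needs at least one eye at T or above, so averaging can never count a patient whom an either-eye rule does not.

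**Step 5: size.** One patient of five is 1/5 = 20 percentage points.

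**Step 6: illustration under assumptions.** Changes in the two eyes were simulated as bivariate normal with mean 0, −3 or −5 mmHg, SD 3 or 4 mmHg and between-eye correlation 0.3, 0.5 or 0.8; all of these are assumed. At T = 5, averaging missed between 38% and 98% of patients with at least one eye up by 5 mmHg or more. With mean 0, SD 3 and correlation 0.5, 2.72% of patients are counted by the mean and 8.42% by either eye. The chance of at least one counted patient in five is then 1 − 0.9728^5 = 12.9% against 1 − 0.9158^5 = 35.6%. The largest miss shares occur where rises are rarest: at mean −5, SD 3 and correlation 0.3 (98% missed), the chance of any either-eye case among five patients is only 0.4%. The conclusion rests on steps 2 to 5, not on this step.

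**The case against.** The strongest reply is that averaging is not the plan for this endpoint. The sentence in Protocol 8.2 sits in a procedure description, is in the past tense and cites a published trial, so it looks like borrowed methods text. It conflicts with the study-eye efficacy analysis. The paragraph's reading rule also differs from footnote f of the Schedule of Activities, which averages three readings. The SAP does not repeat it. This stands: a reader might infer that the sponsor has chosen to average, and the documents do not show that. They show an undefined rule, with averaging as the only per-patient candidate not reserved for efficacy. Apparent borrowing is a reason to limit the sentence, since nothing else fills the gap.

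A reader might also infer that a large one-eye rise would go unnoticed in the trial. The documents do not support that. Eyes are tested separately, IOP is a safety variable in its own right with the eye as default unit, clinically significant abnormal findings become adverse events (8.2), and line listings are planned (9.4.7). Protocol 6.5.1 also acts at 10 mmHg above baseline, although it does not name the eye. With five patients every record can be read. None of this corrects the reported percentage.

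A third tempting inference is that a one-eye rise is to be expected when a lens is lost, because Protocol 7.1 lets a patient continue with one lens. Baseline is untreated IOP after any washout (Protocol 5.1), so an eye without its lens would be expected to drift back towards zero change, not 5 mmHg above it. The provision shows only that the two eyes can differ in exposure.

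Finally, any explicit rule would remove the ambiguity, so the either-eye choice is partly judgement. That is fair. However, averaging and the study-eye rule can each drop a rise in a treated eye, and the either-eye rule cannot.

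**Conclusion.** The point holds in conditional form. The endpoint lacks an eye-to-patient rule, and the only per-patient change rule on paper would, if applied, leave out one-eye rises below 2T − f. With the fellow eye unchanged, a rise of 10 mmHg or more is still counted at the 5 mmHg cut-off; missing a larger rise requires a fall in the fellow eye, and the size of that fall is assumed here. The direction (undercount only) and the step of 20 percentage points per patient follow from the documents. How often it would happen cannot be derived from them. This is worth correcting because the study's purpose is safety, but it affects one secondary endpoint in a descriptive study, and the underlying data remain visible elsewhere.

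**What to change.** In Protocol 9.4.2 and in SAP 5.2 and 6.8, state that a patient is counted at a visit if either treated eye meets the cut-off, and add a table by eye next to the patient percentage. In Protocol 8.2, state that the averaging sentence does not apply to this endpoint, nor to the study-eye efficacy analysis with which it conflicts. If only the SAP is changed, record this under SAP 1.1.

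Separately, reconcile the cut-off between Protocol Section 3 (10 mmHg) and the synopsis, Protocol 9.4.2 and SAP 5.2 and 6.8 (5 mmHg). The combining rule is needed at either value.

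The cost is a few sentences and one small table. No new data are needed, because each eye is already measured separately. The one drawback for the sponsor is that the reported percentage may be slightly less favourable.

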#### 9.4.3 EFFICACY ANALYSES

The secondary efficacy endpoint is the change from baseline in IOP at each visit.

The efficacy analyses will be based on the mITT population and only the study eyes will be used. Statistical analyses will be performed using methods described in Section 9.4.1.

---

#### 9.4.4 BASELINE DESCRIPTIVE STATISTICS

Baseline and demographic assessments will be presented descriptively.

---

#### 9.4.5 PLANNED INTERIM ANALYSES

No interim analysis will be performed.

---

#### 9.4.6 SUB-GROUP ANALYSES

No subgroup analyses are planned.

---

#### 9.4.7 TABULATION OF INDIVIDUAL PATIENT DATA

Line listings will be provided for each patient.

---

#### 9.4.8 OTHER EXPLORATORY ANALYSES

No other exploratory analyses are planned.

---

## 10 SUPPORTING DOCUMENTATION AND OPERATIONAL CONSIDERATIONS

---

### 10.1 REGULATORY, ETHICAL, AND STUDY OVERSIGHT CONSIDERATIONS

---

#### 10.1.1 INFORMED CONSENT PROCESS

---

##### 10.1.1.1 CONSENT AND OTHER INFORMATIONAL DOCUMENTS PROVIDED TO PATIENTS

Consent forms describing in detail the study intervention, study procedures, and risks, that have been reviewed and approved by the relevant IRB, will be given to the patient and written documentation of informed consent will be required prior to starting study intervention. An informed consent form will be submitted with this protocol.

---

##### 10.1.1.2 CONSENT PROCEDURES AND DOCUMENTATION

Informed consent is a process that is initiated prior to the individual's agreeing to participate in the study and continues throughout the individual's study participation. Consent forms will be IRB-approved, and the patient will be asked to read and review the document. The investigator will explain the research study to the patient and answer any questions that may arise. A verbal explanation will be provided in terms suited to the patient's comprehension of the purposes, procedures, and potential risks of the study and of their rights as research patients. Patients will have the opportunity to carefully review the written consent form and ask questions prior to signing. The patients should have the opportunity to discuss the study with their family or surrogates or think about it prior to agreeing to participate. Patients must be informed that participation is voluntary and that they may withdraw from the study at any time, without prejudice.

A copy of the informed consent document will be given to the patients for their records. The informed consent process will be conducted and documented in the source document (including the date), and the form signed, before the patient undergoes any study-specific procedures. The rights and welfare of the patients will be protected by emphasizing to them that the quality of their medical care will not be adversely affected if they decline to participate in this study.

---

### 10.1.2 STUDY DISCONTINUATION AND CLOSURE

Recruitment may be halted by the site investigator at any time for safety reasons. If this occurs, the IRB and any other investigators will be immediately notified.

Leo Lens Technology may stop the study (and/or the study site) for any reason with appropriate notification. If the study is prematurely terminated or suspended, the Principal Investigator will promptly inform study patients, the IRB, and Sponsor and will provide the reason(s) for the termination or suspension. Study patients will be contacted, as applicable, and be informed of changes to study visit schedule.

Study may resume once concerns about safety, protocol compliance, and data quality are addressed, and satisfy the Sponsor, IRB, and/or FDA.

---

### 10.1.3 CONFIDENTIALITY AND PRIVACY

A report of the results of this study may be published or sent to the appropriate health authorities in any country in which the study drug may ultimately be marketed, but the patient's name will not be disclosed in these documents. The patient's name may be disclosed to Leo Lens Technology, the governing health authorities, or the FDA if they inspect the study records as required by law. Appropriate precautions will be taken to maintain confidentiality of medical records and personal information.

In accordance with HIPAA requirements, additional purposes of this study include (1) the publishing of anonymous patient data from the study, and (2) the creation and maintenance of a data repository.

All study-related correspondence, patient records (ie, source documents listed in Section 11.4.1), informed consent forms, patient privacy documentation, records of the distribution and use of all investigational products, and patient questionnaires, correspondence with IRB, and other essential documents should be maintained on file. Local regulatory requirements should be followed regarding the retention of clinical study documentation.

Leo Lens Technology requires that it be notified in writing if the investigator wishes to relinquish ownership of the data so that mutually agreed-upon arrangements can be made for transfer of ownership to a suitably qualified, responsible person.

---

### 10.1.4 FUTURE USE OF STORED SPECIMENS AND DATA

Not applicable.

---

#### 10.1.6 SAFETY OVERSIGHT

No internal data review committee will be used during this study.

---

#### 10.1.7 CLINICAL MONITORING

Clinical site monitoring is conducted to ensure that the rights and well-being of trial patients are protected, that the reported trial data are accurate, complete, and verifiable, and that the conduct of the trial is in compliance with the currently approved protocol/amendment(s), with ICH GCP, and with applicable regulatory requirement(s).

- Monitoring for this study will be performed by an employee of Trial Runners on a periodic basis. The determination of the extent and nature of monitoring will be based on considerations, such as the objective, purpose, design, complexity, masking, size, and endpoints of the study.
- An employee of Trial Runners or regulatory authority representatives will conduct on-site visits to review, audit, and copy study-related documents. These representatives will meet with the investigator and appropriate staff at mutually convenient times to discuss study-related data and questions.

---

#### 10.1.8 QUALITY ASSURANCE AND QUALITY CONTROL

Each clinical site will perform internal quality management of study conduct, data collection, documentation and completion.

Quality control (QC) procedures will be implemented beginning with the data entry system and data QC checks that will be run on the database will be generated. Any missing data or data anomalies will be communicated to the site for clarification/resolution.

Following written Standard Operating Procedures, the monitors will verify that the clinical trial is conducted and data are generated and biological specimens are collected, documented (recorded), and reported in compliance with the protocol, ICH GCP, and applicable regulatory requirements (eg, Good Laboratory Practices, Good Manufacturing Practices).

The investigational site will provide direct access to all trial-related sites, source data/documents, and reports for the purpose of monitoring and auditing by the Sponsor, and inspection by local and regulatory authorities.

---

#### 10.1.9 DATA HANDLING AND RECORD KEEPING

---

##### 10.1.9.1 DATA COLLECTION AND MANAGEMENT RESPONSIBILITIES

Data collection is the responsibility of the clinical trial staff at the site under the supervision of the site investigator. The investigator is responsible for ensuring the accuracy, completeness,

legibility, and timeliness of the data reported. All source documents should be completed in a neat, legible manner to ensure accurate interpretation of data.

- Clinical data will be entered into eCRFs. Data entered into the eCRF will correspond with and be supported by source documentation maintained at the site. A final report of all patient data will be provided to each site at the end of the study to serve as eCRF documentation.

Source documents may include a patient's medical records, diaries, hospital charts, clinic charts, the investigator's patient study files, as well as the results of diagnostic tests and laboratory tests. The investigator's copy of the eCRFs serves as part of the investigator's record of a patient's study-related data.

The following information should be entered into the patient's medical record:

- Patient's name (this information will not be included in the study database)
- Patient's contact information (this information will not be included in the study database)
- Date that the patient entered the study, patient number, and patient medication kit number
- Study title and/or the protocol number of the study and the name of Leo Lens Technology
- Statement that informed consent was obtained (including the date) prior to any study procedures being performed and that the patient was provided a copy of the signed informed consent. A statement that country and local patient privacy-required documentation for this study has been obtained (including the date)
- Dates of all patient visits
- All concurrent medications (List all prescription and non-prescription medications being taken at the time of enrollment. At each subsequent visit, changes to the list of medications should be recorded.)
- Occurrence and status of any AEs (including any procedure-related AEs)
- The date the patient exited the study, and a notation as to whether the patient completed the study or reason for discontinuation
- The results, if applicable, of any procedures performed to confirm eligibility criteria
- Documentation of the patient's medical history
- Heart rate and blood pressure
- Results of biomicroscopy/ophthalmoscopy exams
- Documentation of whether any procedure, including study treatment administration, was performed according to the protocol, noting any deviations (if applicable)
- Study drug accountability and reconstitution records

---

